## Introduction and study rationale

Diabetes Mellitus (DM) is a major concern in South Africa, with an estimated prevalence (by the International Diabetes Federation [IDF]) of 7% in adults between the ages of 20-79 (IDF, 2015). A study in the Western Cape showed a crude prevalence of diabetes of 28.2%, with undiagnosed type 2 DM (DMII) present in 18.1%. (Erasmus et al., 2012). The true prevalence is not known, and undiagnosed DM is a growing burden.

Poorly controlled DM is known to have an adverse effect on the perioperative clinical course with an increase in the length of hospital stay and increased morbidity and mortality (Barker et al., 2015, Underwood et al., 2014). As anaesthesiologists and perioperative medicine practitioners, perioperative glycaemic control falls within our scope of practice. We know there are patients presenting for elective surgery with undiagnosed DMII and impaired fasting glucose levels, however, we are not sure of the prevalence rates. The motivation for this study was thus, to examine fasting blood glucose levels in elective, non-cardiac, non-obstetric pre-operative patients at seven hospitals across the Western Cape. The study will be conducted over the course of one week, to establish the prevalence of both diagnosed and undiagnosed DMII, as well as impaired fasting glucose.

A fasting blood glucose level (defined as a glucose test taken after eight or more hours of no caloric intake) (Sebranek et al., 2013) is a recognised diagnostic test for DMII; patients scheduled for elective surgery are starved for a minimum of six hours. However, a large number of patients are starved for a greater period of time; therefore the majority will fulfil the criteria for a fasting blood glucose test. In this regard, the immediate preoperative period represents an ideal time to check blood glucose levels.

In addition, data will be collected regarding patient comorbidities, as well as evidence of diabetic target organ damage. It is hoped that this collected data will help raise the awareness regarding the contribution of diabetes to the burden of disease, and may aid in establishing an effective perioperative referral system in the screening, diagnosis, and referral for further management of DM.

The aim of this study is to identify the prevalence of abnormal fasting blood glucose levels in preoperative patients in the Western Cape.

Primary outcomes:

- a. Incidence of DM and intermediate hyperglycaemia.

Secondary outcomes:

1. Establish prevalence of adequate control of DM (HbA1C).
2. Establish prevalence of compliance with therapy.
3. Establish proportion of patients with complications of diabetes.

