## Study Methods

All patients will be assessed as part of the routine preoperative evaluation, usually occurring the day before the surgery is scheduled. Informed consent will be obtained by the anaesthetist from eligible patients who agree to participate in the study. The patient will be given the option to withdraw from the study at any time. If a patient chooses not to participate, surgery will proceed as scheduled. Information will be gathered directly from the patient, as well as from the folder and documented on the data Case Report Form (CRF).

At the preoperative assessment, clinical data will be collected and recorded on the CRF. This will include whether the patient is a known diabetic or has intermediate hyperglycaemia. In addition, patients medications, comorbidities, and the planned surgery will be documented.

[figure not shown]
On the day of surgery, before induction of anaesthesia, all patients will have a finger prick blood glucose level done by point of care glucometry, if there is not a documented fasting blood glucose value in their ward file. In patients of unknown diabetic status, should the preoperative value be  $>7$  mmol/l, blood will be drawn when IV access is established, for HbA1C measurement.

In known diabetics, a sample will be taken for HbA1C, regardless of the preoperative fasting blood glucose level, unless there is an HbA1C measurement in the previous 3 months. However, should the patient management have been modified based on the HbA1C result, a repeat HbA1C measurement would be performed. These patients will then be stratified into four categories (based on the WHO diagnostic criteria) (WHO, 2011):

- Low fasting glucose level:  $<2.8$  mmol/l
- Normal fasting glucose level: 2.9-6.0 mmol/l

- Impaired fasting glucose: 6.1-6.9 mmol/l
- Diabetic:  $\geq 7.0$  mmol/l

The study protocol can be summarised in the following flow diagram.

*\*Recent HBA1C (within the previous 3 months). If patient management has been modified in the previous 3 months, a repeat HbA1C measurement would be performed*

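### Fasting glucose is defined as eight hours or more without calories, but the fasting bands behind the primary outcome carry no condition on hours fasted

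*Protocol*

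**What the plan says.** In the diabetes protocol, the Introduction and study rationale gives the fasting test a definition: "defined as a glucose test taken after eight or more hours of no caloric intake". It continues that "patients scheduled for elective surgery are starved for a minimum of six hours", notes that many go without food for longer, and concludes "therefore the majority will fulfil the criteria for a fasting blood glucose test".

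Study Methods then says that on the day of surgery "all patients will have a finger prick blood glucose level done by point of care glucometry". An existing result can replace this test, since it is required only "if there is not a documented fasting blood glucose value in their ward file". The classification step reads "These patients will then be stratified into four categories". One of those bands is "Impaired fasting glucose: 6.1-6.9 mmol/l", and readings of 7.0 mmol/l or more are labelled diabetic. The data items listed for the preoperative visit are diabetic status, medications, comorbidities and planned surgery.

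For HbA1C the same section does set a window in known diabetics: a sample is taken "unless there is an HbA1C measurement in the previous 3 months". In patients of unknown status, HbA1C is drawn only when the glucose exceeds 7 mmol/l.

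The aim is the prevalence of abnormal fasting glucose, and the primary outcome is DM and intermediate hyperglycaemia. The Study Population section sets no fasting criterion.

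**The concern.** The protocol concedes that a minority of readings will not meet its own definition of fasting, and then gives no rule for them. Followed as written, the plan judges a reading at six and a half hours against cut-offs meant for a fast of eight hours or more, and counts the result in the primary outcome.

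The patients exposed are mainly those not already known to be diabetic, because known diabetics are identified by history. For the others the glucose reading decides between normal, impaired and diabetic. A misclassified reading also has a consequence outside the analysis: Ethical considerations sends patients with newly found abnormal values for referral.

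A later analysis plan could apply the eight-hour definition only if the times had been recorded. Collection lasts one week and the CRFs carry no patient identifiers, so times left off the form may not be recoverable.

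**Working it through.** **1. The text, side by side**

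| Step | Where | Condition on hours fasted |
|---|---|---|
| Definition of fasting glucose | Introduction and study rationale | 8 h or more |
| Usual starvation before surgery | Introduction and study rationale | at least 6 h, described as practice |
| Share expected to qualify | Introduction and study rationale | a majority, no figure |
| Eligibility | Study Population | none |
| Who is tested | Study Methods | none |
| Assignment to fasting bands | Study Methods | none |
| Ward-file value used instead | Study Methods | must be a fasting value; no date window |

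No row after the third removes or separates readings taken at 6 to under 8 hours.

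**2. The plan's own precision figure**

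Inputs from Statistical analysis: n = 500, p = 30%. Half-width = 1.96 × √(p(1 − p)/n) = 1.96 × √(0.21/500) = 4.0 points, so 26.0% to 34.0%, a width of 8.0. The protocol states 25 to 34%, a width of about 9. Wilson (26.1 to 34.2) and Clopper-Pearson (26.0 to 34.2) do not give that either. The mismatch is small and separate from this point; 4.0 is used below as the yardstick for random error.

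**3. Possible size of the error**

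The documents give neither f, the share fasted 6 to under 8 hours, nor d, the extra chance of an abnormal reading in those patients. Both are assumptions, and so is the upward direction. Inflation of abnormal-glucose prevalence = f × d:

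| f | d = 5 points | d = 15 points |
|---|---|---|
| 10% (50 patients) | 0.5 | 1.5 |
| 30% (150 patients) | 1.5 | 4.5 |

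These values apply the uplift to all 500 patients. Known diabetics count as DM whatever the reading, so with a known share k the inflation is f × d × (1 − k). Two illustrations:

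- The community survey cited in the introduction has 28.2% diabetic and 18.1% undiagnosed. If both are shares of the whole sample, k = 10.1% and the range is 0.5 × 0.899 = 0.4 to 4.5 × 0.899 = 4.0 points.
- If the whole planning prevalence were already known, k = 30% and the range is 0.5 × 0.70 = 0.35 to 4.5 × 0.70 = 3.15 points.

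**4. Precision if short fasts are set aside**

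Half-width = 1.96 × √(0.21/(500 × (1 − f))):

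- f = 10%: n = 450, 4.2 points
- f = 20%: n = 400, 4.5 points
- f = 30%: n = 350, 4.8 points
- f = 49%, the limit of a majority: n = 255, 5.6 points

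**The case against.** The strongest reply is that the protocol never says a reading under eight hours is to be classified. Six hours is described as usual practice and is not a threshold. The bands are labelled as fasting bands. The sentence that introduces them follows the paragraph on known diabetics, so its reference is unclear. The flow diagram and the CRF are not visible and might deal with fasting time, and a rule on which readings to analyse could sit in an analysis plan.

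Part of this stands. Six hours should not be called a protocol threshold, and the CRF may already hold the times. But the bands make sense only if they apply to all tested patients, and the text attaches no fasting condition to testing or to classification. An analysis plan cannot apply a condition to times that were never recorded.

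A second reply is that HbA1C, which does not depend on fasting, protects the new diabetes diagnoses. It may do so in part. However, it is drawn in unknown-status patients only above 7 mmol/l, no passage says that it overrides the glucose class, and it does not reach the 6.1 to 6.9 band.

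Three stronger readings are tempting and are not supported:

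- A reader might infer that ward-file values of any date are accepted. The protocol requires a documented fasting value, and the ward file may mean the current admission. What is missing is a stated window, such as HbA1C has here and haemoglobin has in the companion anaemia proposal (three months, most recent result).
- A reader might infer that comparisons between hospitals or list positions are distorted. Statistical analysis plans no such comparison.
- A reader might take over-counting as established. A higher reading after a shorter fast is plausible, but neither its direction nor its size can be derived from the documents.

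**Conclusion.** The point holds: the eight-hour definition is not carried through to the rules that produce the primary outcome. Readings after 6 to under 8 hours can be classed as impaired fasting glucose or diabetic, chiefly in patients not known to be diabetic, and HbA1C leaves the impaired band unchecked.

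The inconsistency follows from the text alone. Its numerical effect does not. Under the assumed ranges it runs from 0.5 points, which is negligible, to 4.5 points, which is slightly more than the 4.0-point sampling half-width, and it is lower once known diabetics are set aside. A larger sample would not remove an error of this kind. It should be settled before data collection because the missing information may not be recoverable afterwards.

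**What to change.** - Record on the CRF, if not already there, the time of last caloric intake and the date and time of the glucose reading.
- Base the primary glucose classification of patients not known to be diabetic on readings at eight hours or more. Report shorter fasts as a separate group, and add a sensitivity analysis that includes all patients.
- State that a ward-file value counts only if it comes from the current preoperative fast and meets the eight-hour definition. Otherwise use the finger-prick test already planned.
- Define the denominator so that short-fasted patients are not dropped while every known diabetic is kept. With k = 10.1% and f = 30% from the working, that would raise the known share to 0.101/(0.101 + 0.899 × 0.70) = 13.8%. One way is to estimate total prevalence as k + (1 − k) × q, with k taken from all patients and q from the qualifying readings in those not known to be diabetic.

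This applies the protocol's own definition and sets no new clinical cut-off. The cost is a few CRF fields and one analysis rule. The primary denominator shrinks: the half-width becomes about 4.2 to 4.8 points instead of 4.0 if 10% to 30% of all patients are set aside. Restricting may also select patients by hospital or list order if fasting time varies with them; comparison with the all-patients analysis would show whether that matters.

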## Methods

### Study Design

This will be a prospective, observational study of adult, non-cardiac, non-obstetric, elective surgical patients conducted over a period of one week.

### Study Population

The study population comprises all adult non-cardiac, non-obstetric patients presenting for elective surgery over a period of one week at following sites: Groote Schuur -, Somerset -, Paarl -, Victoria -, Mitchell's Plain -, Worcester - and George Hospital. The study population sample size is estimated to be 500 patients, from a recent study on hypertension carried out at these hospitals.

Inclusion criteria:

- Adult patients presenting for non-cardiac, non-obstetric, elective surgery

Exclusion criteria:

- Paediatric surgical patients
- Cardiac surgical patients
- Obstetric patients
- Emergency surgery

## Study Methods

All patients will be assessed as part of the routine preoperative evaluation, usually occurring the day before the surgery is scheduled. Informed consent will be obtained by the anaesthetist from eligible patients who agree to participate in the study. The patient will be given the option to withdraw from the study at any time. If a patient chooses not to participate, surgery will proceed as scheduled. Information will be gathered directly from the patient, as well as from the folder and documented on the data Case Report Form (CRF).

At the preoperative assessment, clinical data will be collected and recorded on the CRF. This will include whether the patient is a known diabetic or has intermediate hyperglycaemia. In addition, patients medications, comorbidities, and the planned surgery will be documented.

[figure not shown]
On the day of surgery, before induction of anaesthesia, all patients will have a finger prick blood glucose level done by point of care glucometry, if there is not a documented fasting blood glucose value in their ward file. In patients of unknown diabetic status, should the preoperative value be  $>7$  mmol/l, blood will be drawn when IV access is established, for HbA1C measurement.

In known diabetics, a sample will be taken for HbA1C, regardless of the preoperative fasting blood glucose level, unless there is an HbA1C measurement in the previous 3 months. However, should the patient management have been modified based on the HbA1C result, a repeat HbA1C measurement would be performed. These patients will then be stratified into four categories (based on the WHO diagnostic criteria) (WHO, 2011):

- Low fasting glucose level:  $<2.8$  mmol/l
- Normal fasting glucose level: 2.9-6.0 mmol/l

- Impaired fasting glucose: 6.1-6.9 mmol/l
- Diabetic:  $\geq 7.0$  mmol/l

The study protocol can be summarised in the following flow diagram.

*\*Recent HBA1C (within the previous 3 months). If patient management has been modified in the previous 3 months, a repeat HbA1C measurement would be performed*

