#### **Inclusion criteria:**

- Adult patients (>18yrs)
- Non-cardiac patients
- Elective surgery

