#### **Exclusion criteria:**

- <18 years of age
- Obstetrics patients

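### Decision limits do not meet at a glucose of 7.0 mmol/l, a glucose of 2.8 mmol/l and, in the anaemia protocol, age 18

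*Protocol*

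**What the plan says.** Diabetes protocol, Study Methods. For patients whose diabetic status is unknown, the HbA1c rule reads: "In patients of unknown diabetic status, should the preoperative value be $>7$ mmol/l, blood will be drawn when IV access is established". Known diabetics follow a different rule: "In known diabetics, a sample will be taken for HbA1C, regardless of the preoperative fasting blood glucose level", with an exception where a recent result exists. Patients are then to be placed in four glucose categories:

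- "Low fasting glucose level: $<2.8$ mmol/l"
- "Normal fasting glucose level: 2.9-6.0 mmol/l"
- "Impaired fasting glucose: 6.1-6.9 mmol/l"
- "Diabetic: $\geq 7.0$ mmol/l"

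Anaemia protocol. The inclusion list has "Adult patients (>18yrs") and the exclusion list has "<18 years of age". The diabetes protocol's own criteria speak only of adults and paediatric patients and give no age in years.

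**The concern.** These limits decide who is sampled, how a patient is classed and who is enrolled. Each should leave every possible value with exactly one outcome, and three of them do not.

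The mismatch at 7.0 matters most because it cannot be repaired afterwards. An analyst can assign a reading of 2.8 to a band once the data are in, but cannot produce an HbA1c that was never drawn in a one-week collection. The mismatch touches only patients of unknown status, so the missing values fall among newly detected cases, at the lowest glucose in their category. HbA1c is the stated measure for the secondary outcome on adequacy of diabetic control. If that outcome is meant to cover new cases as well as known ones, its denominator is incomplete by rule.

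The age gap leaves staff at seven hospitals to decide for themselves about 18-year-olds. Different sites may decide differently.

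**Working it through.** The plan states no figure on this point, so there is none to reproduce. The check runs every possible value through the rules as written.

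**Inputs** (all from the Protocol)

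- HbA1c trigger, unknown status: glucose > 7 mmol/l (diabetes protocol, Study Methods)
- Categories: low < 2.8; normal 2.9 to 6.0; impaired 6.1 to 6.9; diabetic ≥ 7.0 mmol/l (same section)
- Age, anaemia protocol: include > 18; exclude < 18 (Inclusion and Exclusion criteria)

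**Glucose at one decimal.** Each value from 1.0 to 30.0 mmol/l in steps of 0.1 was tested for membership of exactly one category, and for being in the diabetic category without meeting the trigger. Reporting to 0.1 mmol/l is an assumption, although the bands are written that way.

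| Reading (mmol/l) | Category | HbA1c drawn if status unknown |
|---|---|---|
| 2.7 | low | no |
| 2.8 | none | no |
| 2.9 | normal | no |
| 6.9 | impaired | no |
| 7.0 | diabetic | no (7.0 > 7 is false) |
| 7.1 | diabetic | yes |

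Over the whole range, 2.8 is the only value without a category, and 7.0 is the only value classed as diabetic without triggering HbA1c.

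**Glucose at two decimals.** The protocol also accepts a fasting value already in the ward file, and the resolution of such values is not stated. In steps of 0.01 from 2.50 to 7.49, the values with no category are 2.80 to 2.89, 6.01 to 6.09 and 6.91 to 6.99. These further gaps arise only if values are recorded to two decimals.

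**Age in whole years, anaemia protocol**

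| Age | Included (> 18) | Excluded (< 18) |
|---|---|---|
| 17 | no | yes |
| 18 | no | no |
| 19 | yes | no |

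**How many patients at 7.0.** The documents do not allow a count. For scale only, take the 18.1% undiagnosed figure that the Introduction cites from a Western Cape study and apply it to the planned 500: 500 × 0.181 = 90.5 new cases. If a share s of these read exactly 7.0, the number without HbA1c is 90.5 × s. At s = 2% this is 90.5 × 0.02 = 1.8; at s = 5% it is 90.5 × 0.05 = 4.5. Both the transfer of 18.1% to surgical patients and the range for s are assumptions. For comparison, the plan's expected interval of 25 to 34% spans (0.34 − 0.25) × 500 = 45 patients.

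**The case against.** The best counter-argument concerns consequence. Classification uses glucose alone, and nowhere does the protocol make HbA1c a condition for counting a case. A reading of 7.0 is diabetic with or without it. That stands. A reader might infer that the mismatch biases diabetes prevalence, and the documents do not support this.

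A reader might also infer that the rule introduces glucose-dependent missingness, or that these patients go without follow-up. Neither goes far. Among patients of unknown status, HbA1c depends on glucose by design, and the mismatch affects one further reading value. The diabetes protocol's Ethical considerations refer every patient with an abnormal fasting glucose who is not already known, so a patient at 7.0 is still sent for further workup. Nothing in the documents says that patients at the limit need a second test more than others, or that the trigger should be read as a rounded whole number.

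The 2.8 gap lies between the low and normal bands, and neither is part of the primary outcome. It affects the tabulation only if someone actually reads 2.8. It does leave unstated whether such a reading counts as abnormal for the referral rule.

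On age, if the inclusion limit means past the 18th birthday, the gap shrinks to that one day. It covers all 18-year-olds only when age is recorded in whole years.

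Finally, the flow diagram is not available here and may state the trigger differently. If it does, the text would still disagree with itself.

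These points limit the size of the problem. They do not remove the three gaps.

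**Conclusion.** The point holds as an internal contradiction with a small effect. As written, a patient of unknown status reading 7.0 mmol/l is classed as diabetic without an HbA1c, a reading of 2.8 mmol/l has no class, and age 18 in the anaemia protocol is neither included nor excluded.

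The prevalence of diabetes does not change at 7.0. The likely loss is HbA1c in a few new cases (number unknown), possibly an unclassified low reading, and possibly differences between sites in enrolling 18-year-olds.

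This rests on three assumptions: glucose is reported to 0.1 mmol/l, age is recorded in whole years, and the four categories apply to all participants. The sentence introducing the categories follows directly on the known diabetics, but a band for impaired fasting glucose makes little sense for them alone. The gaps are still worth closing before data collection, because an HbA1c not drawn that week cannot be recovered and the correction costs almost nothing.

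**What to change.** - Reconcile the HbA1c trigger for patients of unknown status with the lower limit of the diabetic category, so that both use the same number and the same inequality. Check the flow diagram and CRF against it. Which limit is right is for the investigators to decide.
- Make the four glucose bands contiguous at the resolution at which values are recorded, and state that resolution, including for values taken from the ward file. Every reading should then fall in exactly one band.
- Write the age limit as one complementary pair (at or above a stated age included, below it excluded) and use it in both protocols, since both recruit from the elective lists of the same seven hospitals.

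The cost is a few characters of protocol and CRF text and a line in the site briefing. Depending on how the trigger is reconciled, there may also be a few additional HbA1c tests.
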